Absorbency Arm: Regular		Test Tampon (N=XX)	Reference Tampon (N=XX)
Visit	Area Examined		
	Assessment Category		
Pre-Use Visit	Perineum (cont'd.)		
Type C Lesions [1]			
Epithelium: Disrupted, superficial		XX (XX.X%)	XX (XX.X%)
Epithelium: Disrupted, deep		XX (XX.X%)	XX (XX.X%)
Blood vessel: Intact		XX (XX.X%)	XX (XX.X%)
Blood vessel: Disrupted		XX (XX.X%)	XX (XX.X%)
Peeling		XX (XX.X%)	XX (XX.X%)
Abrasion		XX (XX.X%)	XX (XX.X%)
Ulceration		XX (XX.X%)	XX (XX.X%)
Laceration		XX (XX.X%)	XX (XX.X%)
Coverage of Lesions [2]			
50% or less		XX (XX.X%)	XX (XX.X%)
Greater than 50%		XX (XX.X%)	XX (XX.X%)
Type D Lesions [1]		XX (XX.X%)	XX (XX.X%)
Coverage of Lesions [2]			
50% or less		XX (XX.X%)	XX (XX.X%)
Greater than 50%		XX (XX.X%)	XX (XX.X%)

Repeat for the following areas examined: Vulva, Urethra, Vagina, Cervix; Repeat for the following visit: Post-Use Visit

Note: Percentages are n/Number of subjects in the Safety Population who belong to the subset of subjects that were selected to undergo gynecological exams within tampon type*100. For the gynecological exam subset, exams were conducted at pre- and post-use visits for each tampon type. Subjects used each tampon type (reference or test) over the course of one menstrual cycle. Pre-use visits were conducted within 72 hours prior to expected menstruation and post-use visits were conducted within 72 hours following the last tampon use for that menstrual cycle.

[1] Subjects are counted only once for each type of lesion.

[2] Subjects are counted only once for the highest coverage lesion recorded for each lesion type.

Reference Listing: 16.2.9.1.1

Programming Note: There will be a pre-use visit and a post-use visit for each tampon type for each subject. Repeat for Absorbency Arm: Super.

AD-ST-33.06 Effective date: 12-Nov-2020

Version Final 1.1 | Date 05-Jun-2023 | AD-PR-109.02 Effective date: 17-Aug-2020

Page 48 of 73

[figure not shown]

Table 14.3.6.1.2
Gynecological Examination – Additional Findings
Safety Population
Gynecological Exam Subset

Absorbency Arm: Regular		Test Tampon (N=XX)	Reference Tampon (N=XX)
Visit	Area Examined Statistic or Category		
Pre-Use Visit			
	Vaginal Discharge – Quantity		
	Scant	XX (XX.X%)	XX (XX.X%)
	Small Amount	XX (XX.X%)	XX (XX.X%)
	Moderate Amount	XX (XX.X%)	XX (XX.X%)
	Profuse	XX (XX.X%)	XX (XX.X%)
	Missing	XX (XX.X%)	XX (XX.X%)
	Vaginal Discharge – Odor		
	Malodorous	XX (XX.X%)	XX (XX.X%)
	Non-Malodorous	XX (XX.X%)	XX (XX.X%)
	Missing	XX (XX.X%)	XX (XX.X%)
	Vaginal Discharge – Color		
	Clear	XX (XX.X%)	XX (XX.X%)
	White	XX (XX.X%)	XX (XX.X%)
	Yellow	XX (XX.X%)	XX (XX.X%)
	Green	XX (XX.X%)	XX (XX.X%)
	Red (Bloody)	XX (XX.X%)	XX (XX.X%)
	Gray	XX (XX.X%)	XX (XX.X%)
	Missing	XX (XX.X%)	XX (XX.X%)

Note: Percentages are n/Number of subjects in the Safety Population who belong to the subset of subjects that were selected to undergo gynecological exams within tampon type*100. For the gynecological exam subset, exams were conducted at pre- and post-use visits for each tampon type. Subjects used each tampon type (reference or test) over the course of one menstrual cycle. Pre-use visits were conducted within 72 hours prior to expected menstruation and post-use visits were conducted within 72 hours following the last tampon use for that menstrual cycle. n is the number of subjects within each category. N is the number of subjects within each article and within absorbency arm.

Subjects XXX,XXX had any abnormal gynecological findings. Subjects XXX,XXX reported any clinically significant gynecological exam result.

Reference Listing: 16.2.9.1.2

Programming Note: There will be a pre-use visit and a post-use visit for each tampon type for each subject. Repeat for Absorbency Arm: Super.

Table 14.3.6.1.2 (cont'd.)
Gynecological Examination – Additional Findings
Safety Population
Gynecological Exam Subset

Absorbency Arm: Regular			
Visit	Area Examined Statistic or Category	Test Tampon (N=XX)	Reference Tampon (N=XX)
Pre-Use Visit			
Vaginal Discharge – Consistency			
Thin		XX (XX.X%)	XX (XX.X%)
Thick		XX (XX.X%)	XX (XX.X%)
Variable		XX (XX.X%)	XX (XX.X%)
Cottage Cheese Like		XX (XX.X%)	XX (XX.X%)
Missing		XX (XX.X%)	XX (XX.X%)
Vaginal pH			
n		XX	XX
Mean (SD)		XX.X (XX.XX)	XX.X (XX.XX)
Median		XX.X	XX.X
Min, Max		XX, XX	XX, XX
Suspected Infection			
Yes		XX (XX.X%)	XX (XX.X%)
No		XX (XX.X%)	XX (XX.X%)
Missing		XX (XX.X%)	XX (XX.X%)

Note: Percentages are n/Number of subjects in the Safety Population who belong to the subset of subjects that were selected to undergo gynecological exam within tampon type*100. For the gynecological exam subset, exams were conducted at pre- and post-use visits for each tampon type. Subjects used each tampon type (reference or test) over the course of one menstrual cycle. Pre-use visits were conducted within 72 hours prior to expected menstruation and post-use visits were conducted within 72 hours following the last tampon use for that menstrual cycle.

Reference Listing: 16.2.9.1.2

Programming Note: There will be a pre-use visit and a post-use visit for each tampon type for each subject. Repeat for Absorbency Arm: Super.

Table 14.3.6.1.2 (cont'd.)
Gynecological Examination – Additional Findings
Safety Population
Gynecological Exam Subset

Absorbency Arm: Regular			
Visit	Area Examined Statistic or Category	Test Tampon (N=XX)	Reference Tampon (N=XX)
Pre-Use Visit			
Other Abnormal Findings			
Yes		XX (XX.X%)	XX (XX.X%)
No		XX (XX.X%)	XX (XX.X%)
Missing		XX (XX.X%)	XX (XX.X%)
Gynecological Exam Result Clinically Significant			
Yes		XX (XX.X%)	XX (XX.X%)
No		XX (XX.X%)	XX (XX.X%)
Missing		XX (XX.X%)	XX (XX.X%)

[figure not shown]
Repeat for the following visit: Post-Use Visit

Note: Percentages are n/Number of subjects in the Safety Population who belong to the subset of subjects that were selected to undergo gynecological exam within tampon type*100. For the gynecological exam subset, exams were conducted at pre- and post-use visits for each tampon type. Subjects used each tampon type (reference or test) over the course of one menstrual cycle. Pre-use visits were conducted within 72 hours prior to expected menstruation and post-use visits were conducted within 72 hours following the last tampon use for that menstrual cycle.

Reference Listing: 16.2.9.1.2

Programming Note: There will be a pre-use visit and a post-use visit for each tampon type for each subject. Repeat for Absorbency Arm: Super.

Statistical Analysis Plan,
Sponsor Kimberly-Clark Corporation
Protocol Number AFC-21-001
PCN Number KIMB228084

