8.2. Diary Responses

The number and percentage of diary responses will be reported for test tampon diary entries and reference tampon diary entries in the Safety population, and separately for each absorbency arm. Diary responses for individual tampon entries will be summarized separately from diary responses following last tampon use. Diary responses for individual tampon entries were reported specific to each tampon used and were recorded repeatedly for each used tampon throughout a given menstrual cycle. The denominator for the percentage calculation for individual tampon entry diary responses will be based upon the total number of used tampon diary entries within each question and within each test article type and within each absorbency arm. The number of tampons remaining white and when the subject reported having any flow when using the tampon will be summarized within each test article type and within each absorbency arm as well. The denominator for the percentage calculation will be the total number of used tampon diary entries within each question and within each test article type and within each absorbency arm. Diary responses recorded following last tampon use were reported only once per menstrual cycle. The reasons for not inserting the tampon using the applicator will be summarized. The denominator for the percentage calculation for diary responses following last tampon use will be based on the total number of diary entries within each question and within each test article type and within each absorbency arm. Individual diary responses and diary responses recorded following the last tampon will be listed. And additionally, the reasons for not inserting the tampon using the applicator will be presented in a separate listing. The 95% CIs for the percentage of patients who are able to insert each tampon will be computed using the exact method (Clopper & Pearson, 1934).

In addition, the testing of equality of proportions of patients who are able to insert each tampon between test and reference article types within each absorbency arm will be performed. For this purpose, the difference between proportions will be calculated along with 95% Wald CIs. Pearson chi-square test will be computed in support of hypothesis testing. The samples for comparison will be considered independent.

The following hypothesis will be tested:

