Absorbency Arm: Regular	Variable Statistic	Test Tampon (N=XX)	Reference Tampon (N=XX)
Length of Elongation			
n [1]		XX	XX
Mean (SD)		XX.X (XX.XX)	XX.X (XX.XX)
Median		XX.X	XX.X
Min, Max		XX, XX	XX, XX
Elongated [2]			
n [1]		XX	XX
Percentage		XX.XX%	XX.XX%
95% CI for the Percentage [3]		XX.XXX%, XX.XXX%	XX.XXX%, XX.XXX%
Difference in Percentage		XX.XX%	
95% CI for the Difference in Percentage [4]		XX.XXX%, XX.XXX%	
Chi-Square		XX.X	
P-Value		X.XXX	

Abbreviations: CI = confidence interval; MITT = modified intent-to-treat; SD = standard deviation.

Note: Percentages are n/Number of used tampons returned by subjects in the MITT Population within tampon type*100. Length is measured in millimeters (mm). Tampon integrity assessments were performed at the post-use visits which were conducted within 72 hours following the last tampon use for that menstrual cycle. Subjects used each test article type (reference or test tampon) over the course of one menstrual cycle. N is the number of subjects within each article and within absorbency arm.

[1] n is the number of tampons.

[2] Any used tampon with a measurement of elongation >10 mm was considered elongated.

[3] The 95% CIs for the percentage elongated estimates were computed using the exact method.

[4] The 95% CIs for the difference in percentage elongated estimates were computed using Wald method

Reference Listing: 16.2.6.1

Programming Note: Repeat for Absorbency Arm: Super.

[figure not shown]

Table 14.2.2.1
 Summary of Individual Tampon Entry Diary Responses
 Safety Population

Absorbency Arm: Regular	Test Tampon (N=XX)	Reference Tampon (N=XX)
Variable Category		
Able to remove the tampon	XX	XX
Yes	XX (XX.X%)	XX (XX.X%)
No	XX (XX.X%)	XX (XX.X%)
White area remaining on tampon	XX	XX
No areas on the tampon remained white	XX (XX.X%)	XX (XX.X%)
Less than half of the tampon remained white	XX (XX.X%)	XX (XX.X%)
About half of the tampon remained white	XX (XX.X%)	XX (XX.X%)
More than half of the tampon remained white	XX (XX.X%)	XX (XX.X%)
Whole product remained white	XX (XX.X%)	XX (XX.X%)
Flow when using the tampon	XX	XX
No flow	XX (XX.X%)	XX (XX.X%)
Spotting only	XX (XX.X%)	XX (XX.X%)
Light	XX (XX.X%)	XX (XX.X%)
Medium	XX (XX.X%)	XX (XX.X%)
Heavy	XX (XX.X%)	XX (XX.X%)
Tampons remaining white and where subject reported having any flow when using the tampon*	XX (XX.X%)	XX (XX.X%)

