Note: Percentages are n/Number of used tampon diary entries recorded by subjects in the Safety Population within each question and within tampon type*100. Subject diaries were returned at the post-use visits which were conducted within 72 hours following the last tampon use for that menstrual cycle. Diary responses for individual tampon entries were reported specific to each tampon used and were recorded repeatedly for each used tampon throughout a given menstrual cycle. Subjects used each test article type (reference or test tampon) over the course of one menstrual cycle.

*Subjects must have reported both the whole product remained white and reported anything other than "No flow". Percentages are n/Number of used tampon diary entries recorded by subjects in the Safety Population that indicate anything other than "No Flow" within tampon type*100.

n is the total number of diary entries for each section of the table. N is the number of subjects within each article and within absorbency arm.

Reference Listing: 16.2.6.2.1

Programming Note: Repeat for Absorbency Arm: Super.

[figure not shown]

Table 14.2.2.2
 Summary of Diary Responses Following Last Tampon Use
 Safety Population

Absorbency Arm: Regular	Test Tampon (N=XX)	Reference Tampon (N=XX)
Variable Category		
Able to open the box to retrieve wrapped tampons	XX	XX
Yes	XX (XX.X%)	XX (XX.X%)
No	XX (XX.X%)	XX (XX.X%)
Able to open each tampon wrapper	XX	XX
Yes	XX (XX.X%)	XX (XX.X%)
No	XX (XX.X%)	XX (XX.X%)
Tampons were clean prior to use	XX	XX
Yes	XX (XX.X%)	XX (XX.X%)
No	XX (XX.X%)	XX (XX.X%)
Able to insert each tampon using the applicator	XX	XX
Yes	XX (XX.X%)	XX (XX.X%)
No	XX (XX.X%)	XX (XX.X%)
Percentage of patients who are able to insert each tampon using the applicator	XX.XX%	XX.XX%
95% CI for the Percentage [1]	XX.XXX%, XX.XXX%	XX.XXX%, XX.XXX%
Difference in Percentage	XX.XX%	
95% CI for the Difference in Percentage [1]	XX.XXX%, XX.XXX%	
Chi-Square	XX.X	
P-Value	X.XXX	
Able to insert each tampon using the applicator (diary #1)	XX	XX
Yes	XX (XX.X%)	XX (XX.X%)
No	XX (XX.X%)	XX (XX.X%)
Able to insert each tampon using the applicator (diary #2)	XX	XX
Yes	XX (XX.X%)	XX (XX.X%)
No	XX (XX.X%)	XX (XX.X%)
Reason why was not able to insert tampon using the applicator	XX	XX
Not able to fully extend the applicator	XX (XX.X%)	XX (XX.X%)
Too hard to push the tampon out of the applicator	XX (XX.X%)	XX (XX.X%)

No tampon in the applicator	XX (XX.X%)	XX (XX.X%)
Applicator was damaged	XX (XX.X%)	XX (XX.X%)

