Other	XX (XX.X%)	XX (XX.X%)

Note: Percentages are n/Number of recorded diary entries by subjects in the Safety Population within each question and within tampon type*100. Subject diaries were returned at the post-use visits which were conducted within 72 hours following the last tampon use for that menstrual cycle. Diary responses recorded following last tampon use were reported only once per menstrual cycle. Subjects used each test article type (reference or test tampon) over the course of one menstrual cycle.

n is the total number of diary entries for each section of the table. N is the number of subjects within each article and within absorbency arm.

[1] The 95% CIs for the percentage of patients who are able to insert each tampon using the applicator and for the difference in percentage of patients who are able to insert each tampon using the applicator were computed using the exact method.

Reference Listing: 16.2.6.2.2

Programming Note: Repeat for Absorbency Arm: Super.

[figure not shown]

Table 14.2.3
 Summary of Packaging and Labeling Interview Responses
 ITT Population
 Gynecological Exam Subset

Variable Category	Overall (N=XX)
Able to correctly identify tampon absorbency provided in the regular absorbency box	XX
Yes	XX (XX.X%)
No	XX (XX.X%)
Able to correctly identify the tampon absorbency ranges for the entire line of products on the box	XX
Yes	XX (XX.X%)
No	XX (XX.X%)
Able to correctly identify the Toxic Shock Syndrome warning on the box	XX
Yes	XX (XX.X%)
No	XX (XX.X%)
Able to correctly identify the information that states how long you should use a tampon on the box	XX
Yes	XX (XX.X%)
No	XX (XX.X%)
Able to correctly identify tampon absorbency provided in the super absorbency box	XX
Yes	XX (XX.X%)
No	XX (XX.X%)
Able to correctly identify tampon absorbency provided in the super plus absorbency box	XX
Yes	XX (XX.X%)
No	XX (XX.X%)

Abbreviation: ITT = intent-to-treat.

Note: Only the subset of subjects who were selected to undergo gynecological exams prior to and following tampon use completed the packaging and labeling interview. The packaging and labeling interview was conducted at the Screening/Baseline Visit (Visit 1). Percentages are n/Number of subjects in the ITT Population who belong to the subset of subjects that were selected to undergo gynecological exams and responded to the respective question *100.

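### SAP 8.2 and the Table 14.2.2.2 footnote name different interval methods for the insertion difference; the reported interval is mislabelled or undefined, and the choice matters only near 100% success

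*SAP*

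**What the plan says.** SAP 8.2 treats two quantities separately. For each product's insertion percentage, the "CIs for the percentage of patients who are able to insert each tampon will be computed using the exact method", with Clopper-Pearson cited. For the comparison of products, "the difference between proportions will be calculated along with 95% Wald CIs", supported by a Pearson chi-square test. On the data structure it says "The samples for comparison will be considered independent".

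The shell for Table 14.2.2.2 in SAP 14.2 marks both the per-product interval row and the difference row with footnote [1]. That footnote says the intervals for the percentages and "for the difference in percentage of patients who are able to insert each tampon using the applicator were computed using the exact method".

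The shell for elongation, Table 14.2.1, has the same layout but two footnotes. Footnote [3] gives the exact method for the percentages. Footnote [4] reads "The 95% CIs for the difference in percentage elongated estimates were computed using Wald method", which agrees with SAP 8.1.

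**The concern.** Within one SAP, the text and the shell give different methods for the same interval. Clopper-Pearson has no form for a difference of two proportions. The footnote therefore either puts the wrong label on a Wald interval or calls for an exact interval whose type is never stated, and the available exact types differ widely.

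A separate weakness lies behind the mismatch. The Wald interval uses the observed variance, which is zero when every response is a success. If insertion succeeds for nearly everyone, the table could print a 95% interval of 0.000% to 0.000%, which claims a certainty the data cannot give. At stake are the reproducibility and honesty of a reported error bar on a key secondary user need.

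**Working it through.** **Inputs.** The documents state no figure for this interval. The only number taken from them is n = 369 per product.
- *Source of 369.* It is the enrolment per absorbency (protocol section 11; SAP 3.2). The arcsine formula reproduces it: h = 2·asin(√0.007) − 2·asin(√0.002) = 0.0781; 2(1.960 + 0.842)²/h² gives 2,577 tampons per type; 2,577/7 rounds up to 369 subjects; 369 × 7 = 2,583.
- *One response per product.* "Diary responses recorded following last tampon use were reported only once per menstrual cycle", so each subject contributes at most one insertion response per product.
- *Independence.* Taken as SAP 8.2 states it.
- *Success counts.* Illustrative, because no expected insertion rate is given.

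**Formulas.**
- Wald: d ± 1.96·√[p₁(1−p₁)/n + p₂(1−p₂)/n].
- Newcombe: with Wilson limits (l, u) for each product, lower = d − √[(p₁−l₁)² + (u₂−p₂)²] and upper = d + √[(u₁−p₁)² + (p₂−l₂)²].
- Exact unconditional: two one-sided tests at 0.025, inverted with the p-value maximised over the nuisance rate, ordered either by the score statistic or by the raw difference.

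**369 vs 369.** The Wald variance is 0, so the interval is 0.0 to 0.0. The Wilson limits are 0.98970 and 1, so Newcombe is 0 ± √[(1 − 0.98970)² + 0²] = ±1.03 points.

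**369 vs 365.** d = 4/369 = 1.084 points.
- Wald: SE = √(0.98916 × 0.01084/369) = 0.539 points; 1.084 ± 1.96 × 0.539 = 0.03 to 2.14.
- Newcombe: Wilson limits for 365/369 are 0.97246 and 0.99578. Lower = 0.01084 − √(0.01030² + 0.00662²) = −0.0014. Upper = 0.01084 + (0.98916 − 0.97246) = 0.0275.
- Score-ordered exact: at zero difference the maximised one-sided p is 0.0232, below 0.025, so the interval excludes 0.

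**354 vs 354 (about 96%).** Wilson limits are 0.93402 and 0.97521 around 0.95935. Newcombe is ±√(0.02533² + 0.01586²) = ±2.99 points.

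| Successes of 369 | Wald | Newcombe | Exact, score-ordered | Exact, raw difference |
|---|---|---|---|---|
| 369 vs 369 | 0.00 to 0.00 | −1.03 to 1.03 | −1.05 to 1.05 | −7.34 to 7.34 |
| 369 vs 365 | 0.03 to 2.14 | −0.14 to 2.75 | 0.02 to 2.77 | −6.26 to 8.42 |
| 354 vs 354 | −2.85 to 2.85 | −2.99 to 2.99 | −3.01 to 3.01 | −7.34 to 7.34 |

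**Chance of a zero-width Wald interval.** Both products must show 369 of 369, so with a common true rate p the chance is p^738: 48% at 99.9%, 23% at 99.8%, 2.5% at 99.5% and 0.06% at 99%.

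**Coverage.** At true rates of 99.8% and 99.6%, the nominal 95% Wald interval covers the true difference 88% of the time.

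**The case against.** The best defence is that this is a copying slip with an obvious reading. SAP 8.2 uses the same scheme as 8.1, and the elongation shell labels the difference as Wald, so a careful programmer would probably produce Wald and only the footnote would be wrong. That is likely. The printed label would still be untrue, though, and neither passage is stated to take precedence.

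The second defence is that nothing turns on the interval, and this stands for the study decision. The diary criterion compares point estimates: at least 96%, or failing that a test rate no lower than the reference rate. SAP 4.1 calls the validation analyses descriptive. A reader might infer that the choice of interval could change whether the user need is validated; the documents do not support that. Nor is the interval the only statement of uncertainty. The same block of the table prints per-product intervals and a chi-square p-value. For 369 vs 365 the pooled rate is 734/738, and the chi-square is 4.02 with p = 0.045.

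Third, the size depends on rates the documents do not give. The 96% threshold is a floor, not a forecast, so it does not show that results will lie near 100%. This also stands, and it is why a range is shown rather than the extreme alone.

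**Conclusion.** The inconsistency is real and should be corrected before reporting. As written, the insertion-difference interval is either mislabelled or undefined. The consequence is limited to that interval.

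With 369 independent responses per product, the methods separate clearly only close to 100% success. At 100% in both products, Wald has no width while the score-type intervals run to about ±1 point. At about 96% the score-ordered exact interval is only some 6% wider than Wald (3.01/2.85).

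A reader might infer that any exact interval would reverse Wald on whether zero difference is excluded. It does not. For 369 vs 365, Wald and the score-ordered exact interval both exclude 0, while Newcombe and the raw-difference exact interval include it. The answer depends on which method is meant, and the SAP does not say.

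These figures rest on full enrolment yielding a response for each product, on the SAP's independence assumption and on assumed success rates. Whether independence suits a cross-over is a separate question that affects all four intervals.

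**What to change.** - In Table 14.2.2.2, restrict footnote [1] to the per-product percentages (Clopper-Pearson). Tag the difference row with a new footnote [2], as Table 14.2.1 does with its own pair.
- Name the same single method for the difference in SAP 8.2 and in footnote [2]. This alone removes the contradiction.
- As a further improvement, make that method the Newcombe score interval for independent proportions in place of Wald, because it does not collapse at 100%.

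The cost is one sentence and one footnote. The downside is a slightly wider interval and a possible borderline mismatch with the Pearson test. The 369 vs 365 example shows one: p = 0.045 beside a Newcombe interval of −0.14 to 2.75. A short note under the table can explain that the two use different variance estimates.

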14.3. Planned Listing Shells

See [Figure 3](#) below.

[figure not shown]

[figure not shown]
Figure 3: Planned Listing Shells

Listing 16.2.1.1
Subject Disposition
All Subjects

Absorbency Arm: XXX					
Subject ID	Subject Status	Date of Completion / Discontinuation (Study Day)	Reason for Discontinuation	If Death, Date of Death (Study Day)/ Cause of Death	If Lost to Follow-Up, Date of Last Contact (Study Day)/ Comment
XXXXXX	XXXXXXXXXXXX	DDMMYY (XX)			
XXXXXX	XXXXXXXXXXXX	DDMMYY (XX)	XXXXXXXXXX		
XXXXXX	XXXXXXX	DDMMYY (XX)	XXXXXXXXXX	DDMMYY (XX)/XXXXXXXXXX	
XXXXXX	XXXXXXX	DDMMYY (XX)	XXXXXXXXXX		DDMMYY (XX)/XXXXXXXXXX

Note: Study day is calculated relative to the date of first insertion of study product (either test or reference tampon).

Programming Note: If reason for discontinuation is present, concatenate reason for discontinuation with specify text, e.g., "Adverse Event: XXXXX". If a secondary cause of death is listed, concatenate to the primary cause of death with a semicolon. Repeat for Absorbency Arm: Regular and Absorbency Arm: Super.

Listing 16.2.2.1
Inclusion and Exclusion Criteria
All Subjects

Absorbency Arm: XXX

Subject ID	Date Screened	Met All Eligibility Criteria?	Criteria Not Met/Reason Not Met
XXXXXX	DDMMYYYYYY	Yes	
XXXXXX	DDMMYYYYYY	Yes	
XXXXXX	DDMMYYYYYY	No	Inclusion #1/XXXXXXXXXXXXXXXXXXXX; Exclusion #9/XXXXXXXXXXXX
XXXXXX	DDMMYYYYYY	Yes	

Programming Note: If there is no "Reason Not Met" included for the corresponding criteria not met, then concatenate the criteria not met with "Reason not given", e.g., "Inclusion #1/Reason not given". If there are multiple criteria met, please list each criteria/reason not met concatenated with a ;. Repeat for Absorbency Arm: Regular and Absorbency Arm: Super. Display screen failures at the end of the listing. For screen failures, the top row will read "Absorbency Arm: Not Assigned (Screen Failures)".

Listing 16.2.2.2
Protocol Deviations
All Subjects

Absorbency Arm: XXX

Subject ID	Any Major Protocol Deviations?	Deviation Occurred During a Time Frame?	Deviation Start Date (Study Day)/Deviation End Date (Study Day)	First Visit Impacted/Last Visit Impacted	Protocol Deviation Category	Description
XXXXXX	No					
XXXXXX	Yes	Yes	DDMMYYYYYY (XX)/ DDMMYYYYYY (XX)	XXXXXXX/ XXXXXXX	XXXXXXXXXX	
		No	DDMMYYYYYY (XX)/ DDMMYYYYYY (XX)	XXXXXXX/ XXXXXXX	XXXXXXXXXX	
XXXXXX	Yes	Yes	DDMMYYYYYY (XX)/ DDMMYYYYYY (XX)	XXXXXXX/ XXXXXXX	XXXXXXXXXX	

Note: Study day is calculated relative to the date of first insertion of study product (either test or reference tampon).

Programming Note: If "Deviation Occurred During a Time Frame?" is "No" then repeat Deviation Start Date (Study) for Deviation End Date (Study Day) and repeat First Visit Impacted for Last Visit Impacted. If there is text for "Additional Description (Other than "NA", "N/A" and similar)", then concatenate that text with the text for "Description", e.g., "DESCRIPTION TEXT XXX. ADDITIONAL TEXT." Repeat for Absorbency Arm: Regular and Absorbency Arm: Super.

Listing 16.2.2.3
Reason for Screen Failures
Screen Failures

Subject ID	Failed Date	Met All Eligibility Criteria?	Criteria Not Met/Reason Not Met
XXXXX	DDMMYYYYYY	No	Inclusion #4/XXXXXXXXXXXXXXXXXXXX; Exclusion #2/XXXXXXXXXXXXXX
XXXXX	DDMMYYYYYY	No	Inclusion #1/XXXXXXXXXXXXXXXXXXXX; Exclusion #9/XXXXXXXXXXXXXX
XXXXX	DDMMYYYYYY	No	Inclusion #8/XXXXXXXXXXXXXXXXXXXX; Exclusion #5/XXXXXXXXXXXXXX
XXXXX	DDMMYYYYYY	No	Inclusion #6/XXXXXXXXXXXXXXXXXXXX; Exclusion #12/XXXXXXXXXXXXXX

Programming Note: If there is no "Reason Not Met" included for the corresponding criteria not met, then concatenate the criteria not met with "Reason not given", e.g., "Inclusion #1/Reason not given". If there are multiple criteria met, please list each criteria/reason not met concatenated with a ";".

Listing 16.2.3.1
Analysis Populations
All Subjects

Absorbency Arm: XXX

Subject ID	Date	Number	Randomization		Analysis Populations				Primary Reason(s) for Exclusion
			Tampon Used	Part of Subset? [1]	ITT [2]	Safety [3]	MITT [4]		
XXXXXX	DDMMYY	XXXX	XXXXXXXX	XXXXXXXX	Yes	No	No	Safety: Subject did not insert any tampons.	
XXXXXX	DDMMYY	XXXX	XXXX	XXXX	Yes	Yes	Yes		
XXXXXX	DDMMYY	XXXX	XXXXXXXX	XXXXXXXX	Yes	Yes	No	MITT: Subject did not return any tampons that could be assessed for elongation.	
XXXXXX	DDMMYY	XXXX	XXXX	XXXXXX	No	No	No	ITT: Subject was not randomized.	

Abbreviations: BR = regular absorbency test tampon; BS = super absorbency test tampon; CR = regular absorbency reference tampon; CS = super absorbency reference tampon; ITT = intent-to-treat; MITT = modified intent-to-treat.

[1] A subset of subjects were selected to undergo gynecological exams prior to and following tampon use. In addition, this subset of subjects completed the packaging and labeling interview at the Screening/Baseline Visit (Visit 1).

[2] The ITT Population includes all subjects randomized into the study.

[3] The Safety Population includes all ITT subjects who insert at least 1 tampon.

[4] The MITT Population includes all subjects in the Safety population who have no major protocol deviations and return at least 1 tampon that can be assessed for elongation.

Programming Note: Repeat for Absorbency Arm: Regular and Absorbency Arm: Super.

Listing 16.2.4.1
Subject Consent and Demographics
All Subjects

Absorbency Arm: XXX							
Subject ID	Date Informed Consent Signed/ Consent Version	Protocol Version	Date of Birth	Age (years)	Sex	Ethnicity	Race
XXXXXX	DDMMYYYY/ XXXXXXXXXX	XXXXXXXXXX	DDMMYYYY	XX	Female	XXXXXX	XXXXXX
XXXXXX	DDMMYYYY/ XXXXXXXXXX	XXXXXXXXXX	DDMMYYYY	XX	Female	XXXXXX	XXXXXX
XXXXXX	DDMMYYYY/ XXXXXXXXXX	XXXXXXXXXX	DDMMYYYY	XX	Unknown	XXXXXX	XXXX
XXXXXX	DDMMYYYY/ XXXXXXXXXX	XXXXXXXXXX	DDMMYYYY	XX	Female	XXXXXX	XXXXXX
XXXXXX	DDMMYYYY/ XXXXXXXXXX	XXXXXXXXXX	DDMMYYYY	XX	Undifferentiated	XXXXXX	XXXXXX

Programming Note: If multiple races are selected, then concatenate all selected races using a semicolon. Repeat for Absorbency Arm: Regular and Absorbency Arm: Super.

Listing 16.2.4.2
 Medical History
 All Subjects

[figure not shown]
Absorbency Arm: XXX

Subject ID	Any Medical History Reported?	Date Medical History Collected (Study Day)	Category/Verbatim Term	Start Date (Study Day)/End Date (Study Day)	Medical History Disease/Condition Under Control?
XXXXXX	Yes	DDMMYYYY (XX)	XXXXXXXXXXXXXX/ XXXXXXXXXXXXXX/ XXXXXXXXXXXXXX	DDMMYYYY (XX)/ DDMMYYYY (XX)	Yes
			XXXXXXXXXXXXXX/ XXXXXXXXXXXXXX/ XXXXXXXXXXXXXX	–MMYYYY / Ongoing	No
XXXXXX	Yes	DDMMYYYY (XX)	XXXXXXXXXXXXXX/ XXXXXXXXXXXXXX/ XXXXXXXXXXXXXX	DDMMYYYY (XX)/ DDMMYYYY (XX)	Yes
			XXXXXXXXXXXXXX/ XXXXXXXXXXXXXX/ XXXXXXXXXXXXXX	–MMYYYY / Ongoing	Yes

Abbreviation: MedDRA = Medical Dictionary for Regulatory Activities.

Note: At the Screening/Baseline Visit (Visit 1), subjects were asked to report any previously ongoing or current medical conditions or procedures that had occurred within 3 months prior to study entry. Medical history was coded using MedDRA version 25.1. Study day is calculated relative to the date of first insertion of study product (either test or reference tampon).

Programming Note: If medical history is ongoing, denote with "Ongoing" rather than the end date. Repeat for Absorbency Arm: Regular and Absorbency Arm: Super.

[figure not shown]
Listing 16.2.4.3
Tampon Use Questionnaire
All Subjects

Absorbency Arm: XXX

Subject ID	Study Visit	Date Completed (Study Day)	Assessment	Result
XXXXX	XXXXXXXX	DDMMYY (XX)	How many total tampons do you typically use during your period? What tampon absorbency do you use most often? Are you willing to use only regular absorbency tampons during your participation in the study, if needed and if you qualify? Are you willing to use only super absorbency tampons during your participation in the study, if needed and if you qualify?	XXX XXX XXX XXX
XXXXX	XXXXXXXX	DDMMYY (XX)	How many total tampons do you typically use during your period? What tampon absorbency do you use most often? Are you willing to use only regular absorbency tampons during your participation in the study, if needed and if you qualify? Are you willing to use only super absorbency tampons during your participation in the study, if needed and if you qualify?	XXX XXX XXX XXX

Note: Study day is calculated relative to the date of first insertion of study product (either test or reference tampon).

Programming Note: If the response for "What tampon absorbency do you use the most?" is "I use approximately equal numbers of 2 or more absorbency tampons" then please concatenate the result with the tampons selected, e.g., "I use approximately equal numbers of 2 or more absorbency tampons: Light; Regular". Repeat for Absorbency Arm: Regular and Absorbency Arm: Super.

Listing 16.2.5.1
Test Article and Diary Dispensation and Diary Training
All Subjects

Absorbency Arm: XXX

Subject ID	Study Visit	Test Article and Diary Dispensation Completed?	Diary Training Performed?/Reason Not Performed	Diary Number	Lot Number of Tampons Dispensed	Tampon Code Dispensed	Dispensation Date (Study Day)
XXXXXX	XXXXXXXXXX	Yes	Yes	XX	XX	XX	DDMMYYYY (XX)
	XXXXXXXXXX	Yes	No/ XXXXXXXXXXXXXX	XX	XX	XX	DDMMYYYY (XX)
XXXXXX	XXXXXXXXXX	Yes	Yes	XX	XX	XX	DDMMYYYY (XX)
	XXXXXXXXXX	No	No/ XXXXXXXXXXXXXX	XX	XX	XX	DDMMYYYY (XX)

Abbreviations: BR = regular absorbency test tampon; BS = super absorbency test tampon; CR = regular absorbency reference tampon; CS = super absorbency reference tampon.

Note: Study day is calculated relative to the date of first insertion of study product (either test or reference tampon).

Programming Note: Repeat for Absorbency Arm: Regular and Absorbency Arm: Super.

Listing 16.2.5.2
Diary Review
Safety Population

Absorbency Arm: XXX

Subject ID	Study Visit	Date Returned (Study Day)	Diary Number	Tampon Code	Diary Entry for Each Tampon Used?	Are All Diary Entries Accurate and Complete?	Were All Discrepancies Addressed and Corrected with Subject?
XXXXXX	XXXXXXXX	DDMMYYYY (XX)	1	XX	Yes	Yes	No; XXXXXXXXXXXXXXXXX
	XXXXXXXX	DDMMYYYY (XX)	2	XX	No	No	
XXXXXX	XXXXXXXX	DDMMYYYY (XX)	1	XX	Yes	No	Yes
	XXXXXXXX	DDMMYYYY (XX)	2	XX	Yes	Yes	

Abbreviations: BR = regular absorbency test tampon; BS = super absorbency test tampon; CR = regular absorbency reference tampon; CS = super absorbency reference tampon.

Note: Study day is calculated relative to the date of first insertion of study product (either test or reference tampon).

Programming Note: If the response for "Were all discrepancies addressed and corrected with the subject?" is "No", then concatenate the text for "If no, please explain", e.g., "No; XXXXXXXXXXXXXXXXX". Repeat for Absorbency Arm: Regular and Absorbency Arm: Super.

Listing 16.2.6.1
 Tampon Integrity Assessment
 Safety Population

[figure not shown]
Absorbency Arm: XXX										
Subject ID	Study Visit	Assessment Performed?/ Reason Not Performed	Assessment Date (Study Day)	Number of Used Tampons Returned	Number of Unused Tampons Returned	Menstrual Cycle	Tampon Code Returned	Tampon Number	Length of Elongation (mm)	Picture Taken of Elongated [1]? Picture Taken of Tampon?
XXXXXX	XXXXXX	No/ XXXXXXXXXXXX								
XXXXXX	XXXXXX	Yes	DDMMYYYY (XX)	XX	XX	XX	XX	XX	No	Yes
						XX	XX	XX	No	Yes
						XX	XX	XX	Yes	Yes
						XX	XX	XX	XX	No
						XX	XX	XX	XX	XX
						XX	XX	XX	XX	XX
						XX	XX	XX	XX	XX
						XX	XX	XX	XX	XX
					
XXXXXX	Yes		DDMMYYYY (XX)	XX	XX	XX	XX	XX	XX	XX
						XX	XX	XX	XX	XX
					

Abbreviations: BR = regular absorbency test tampon; BS = super absorbency test tampon; CR = regular absorbency reference tampon; CS = super absorbency reference tampon.

Note: Study day is calculated relative to the date of first insertion of study product (either test or reference tampon).

[1] Any used tampon with a measurement of elongation >10 mm was considered elongated.

Programming Note: Repeat for Absorbency Arm: Regular and Absorbency Arm: Super.

[figure not shown]
Listing 16.2.6.2.1
 Individual Tampon Entry Diary Responses
 Safety Population

Absorbency Arm: XXX

Subject ID	Study Visit	Diary Number	Tampon Code	Entry Number	Date/Time (Study Day) Tampon Inserted	Date/Time (Study Day) Tampon Removed	Able to Remove Tampon?	White Area Remaining on Tampon?	Flow When Using Tampon?	Comments
XXXXXX	XXXXXXX	1	XX	XX	DDMMYY/HH:MM (XX)	DDMMYY/HH:MM (XX)	XX	XXXXXX	XXXX	
				XX	DDMMYY/HH:MM (XX)	DDMMYY/HH:MM (XX)	XX	XXXXXX	XXXX	XXXXXX
				XX	DDMMYY/HH:MM (XX)	DDMMYY/HH:MM (XX)	XX	XXXXXX	XXXX	
				XX	DDMMYY/HH:MM (XX)	DDMMYY/HH:MM (XX)	XX	XXXXXX	XXXX	XXXXXX
XXXXXX	XXXXXXX	2	XX	XX	DDMMYY/HH:MM (XX)	DDMMYY/HH:MM (XX)	XX	XXXXXX	XXXX	
				XX	DDMMYY/HH:MM (XX)	DDMMYY/HH:MM (XX)	XX	XXXXXX	XXXX	XXXXXX
				XX	DDMMYY/HH:MM (XX)	DDMMYY/HH:MM (XX)	XX	XXXXXX	XXXX	
XXXXXX	XXXXXXX	1	XX	XX	DDMMYY/HH:MM (XX)	DDMMYY/HH:MM (XX)	XX	XXXXXX	XXXX	
				XX	DDMMYY/HH:MM (XX)	DDMMYY/HH:MM (XX)	XX	XXXXXX	XXXX	XXXXXX
			

Abbreviations: BR = regular absorbency test tampon; BS = super absorbency test tampon; CR = regular absorbency reference tampon; CS = super absorbency reference tampon.
 Note: Study day is calculated relative to the date of first insertion of study product (either test or reference tampon).

Programming Note: Repeat for Absorbency Arm: Regular and Absorbency Arm: Super.

Listing 16.2.6.2.2
 Diary Responses Following Last Tampon Use
 Safety Population

[figure not shown]
Absorbency Arm: XXX

Subject ID	Study Visit	Diary Number	Tampon Code	Assessment	Response
XXXXXX	XXXXXXX	1	XX	Were you able to open the box to retrieve the wrapped tampons? Were you able to open each tampon wrapper? Were each of the tampons clean prior to using them? Were you able to insert each tampon using the applicator?	Yes Yes Yes Yes
	XXXXXXX	2	XX	Were you able to open the box to retrieve the wrapped tampons? Were you able to open each tampon wrapper? Were each of the tampons clean prior to using them? Were you able to insert each tampon using the applicator?	Yes No; XXXXXXXXXXXX Yes No
XXXXXX	XXXXXXX	1	XX	Were you able to open the box to retrieve the wrapped tampons? Were you able to open each tampon wrapper? Were each of the tampons clean prior to using them? Were you able to insert each tampon using the applicator?	Yes Yes Yes Yes
XXXXXXX

Abbreviations: BR = regular absorbency test tampon; BS = super absorbency test tampon; CR = regular absorbency reference tampon; CS = super absorbency reference tampon.

Programming Note: If the response for any of the assessments "Were you able to open the box to retrieve the wrapped tampons?", "Were you able to open each tampon wrapper?", or "Were each of the tampons clean prior to using them?" is "No" then concatenate the text from the corresponding "If no, please explain in detail", e.g., "No; XXXXXXXXXXXX". If the response for the assessment "Were you able to insert each tampon using the applicator?" is "No", then keep it as 'No' without the details.

Repeat for Absorbency Arm: Regular and Absorbency Arm: Super.

Listing 16.2.6.2.3
Reason for Not Inserting the Tampon Using the Applicator
Safety Population

Absorbency Arm: XXX

Subject ID	Study Visit	Diary Number	Tampon Code	Reason	Explain in Detail, Why You Were Not Able to Insert Each Tampon Using the Applicator	Comments
XXXXXX	XXXXXXX	1	XX	XXXX; XXXX	XXXXXXXXXXXXXXXXXXXXXXXXXXXXXX	XXXXXXXXXXXXXX
	XXXXXXX	2	XX	XXXX; XXXX	XXXXXXXXXXXXXXXXXXXXXXXXXXXXXX	XXXXXXXXXXXXXX
XXXXXX	XXXXXXX	1	XX	XXXX; XXXX	XXXXXXXXXXXXXXXXXXXXXXXXXXXXXX	XXXXXXXXXXXXXX
XXXXXX	XXXXXXX

Abbreviations: BR = regular absorbency test tampon; BS = super absorbency test tampon; CR = regular absorbency reference tampon; CS = super absorbency reference tampon.

Programming Note: Repeat for Absorbency Arm: Regular and Absorbency Arm: Super.
In case of several reasons, please concatenate them by ";".

Listing 16.2.6.3
Packaging and Labeling Interview
Gynecological Exam Subset

Absorbency Arm: XXX

Subject ID	Study Visit	Assessment Performed?/ Reason Not Done	Assessment Date (Study Day)	Interviewer Initials	Assessment	Response
XXXXXX	XXXXXXX	No/XXXXXXXX				
